# **Glossary of terms**

[figure not shown]
Additional treatment	Medicinal products that may be used during the clinical trial as described in the protocol, but not as an investigational medicinal product (e.g. any background therapy)
Assessment	A procedure used to generate data required by the study
Biologic Samples	A biological specimen including, for example, blood (plasma, serum), saliva, tissue, urine, stool, etc. taken from a study participant
Clinical Outcome Assessment (COA)	A measure that describes or reflects how a participant feels, functions, or survives
Clinical Trial Team	A group of people responsible for the planning, execution and reporting of all clinical trial activities. Examples of team members include the Study Lead, Medical Monitor, Trial Statistician etc.
Coded Data	Personal Data which has been de-identified by the investigative center team by replacing personal identifiers with a code.
Cohort	A group of individuals who share a common exposure, experience or characteristic, or a group of individuals followed-up or traced over time
Control drug	A study drug (active or placebo) used as a comparator to reduce assessment bias, preserve blinding of investigational drug, assess internal study validity, and/or evaluate comparative effects of the investigational drug
Discontinuation from study	Point/time when the participant permanently stops receiving the study treatment and further protocol required assessments or follow-up, for any reason. No specific request is made to stop the use of their samples or data.
Discontinuation from study treatment	Point/time when the participant permanently stops receiving the study treatment for any reason (prior to the planned completion of study drug administration, if any). Participant agrees to the other protocol required assessments including follow-up. No specific request is made to stop the use of their samples or data.
Dosage	Dose of the study treatment given to the participant in a time unit ( )
Electronic Data Capture (EDC)	EDC is the electronic acquisition of clinical study data using data collection systems, such as Web-based applications, interactive voice response systems and clinical laboratory interfaces. EDC includes the use of Electronic Case Report Forms (eCRFs) which are used to capture data transcribed from source data/documents used at the point of care

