### 6.5 **Treatment blinding**

Participants, investigator staff (including OHPs), persons performing the assessments, and the Novartis Clinical Trial Team (CTT) will remain blinded to the identity of the treatment from the time of randomization until database lock except for unblindings listed in Table 6-3.

Unblinding a single participant at site for safety reasons (necessary for participant management) will occur via an emergency system in place at the site. As a result, the participant should be discontinued from the study treatment.

The DMC members will be un-blinded as per the procedures described in the DMC charter.

The randomization codes associated with participants from whom PK samples are taken will be disclosed to PK analysts who will keep PK results confidential until database lock. Randomization codes may be also disclosed to biomarker analysts (concerned with target engagement markers or pathway engagement markers) who also will keep the blind.

The following method will be used to maintain the blind:

the identity of the treatments will be concealed by the use of study treatment that are all identical in packaging, labeling, schedule of administration, appearance, taste, and odor.

At the time of safety review/interim analysis for efficacy, the Novartis CTT may create and review unblinded interim reports.

Table 6-3 Blinding and unblinding plan

Role		Time o	r Event	
	Randomization list generated	Treatment allocation & dosing	Safety event (single subject unblinded)	Interim Analysis & dose escalation
Participants	В	В	UI	В
Site staff	В	В	UI	В
Unblinded site staff (see text for details)	В	UI	UI	UI
Drug Supply and Randomization Office	UI	UI	UI	U
Statistician/statistical programmer/data analysts	В	В	UI	UI
Independent committees used for assessing interim results	В	UI	UI	UI
All other sponsor staff not identified above	В	В	UI	UI
Unblinded sponsor staff (see text for details)	В	UI	UI	UI

B Remains blinded

NA Not applicable

UI Allowed to be unblinded on individual patient level

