#### 10.3 Committees

## 10.3.1 **Data monitoring committee**

This study will include a data monitoring committee (DMC) which will function independently of all other individuals associated with the conduct of this clinical trial, including the site investigators participating in the study. Note: the trial statistician will be employed as a member of the DMC. The DMC will assess at defined intervals the progress of the clinical trial, safety

data and critical efficacy variables, and recommend to Novartis whether to continue, modify or terminate a trial.

Specific details regarding composition, responsibilities, data monitoring, and meeting frequency and documentation of DMC reports, minutes and recommendations will be described in a separate charter that is established between Novartis and the DMC.

The DMC will also advise the Sponsor in case an unplanned safety review is triggered and requires a decision to stop or continue the study (as per Section 9.3).

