## 11.2 Database management and quality control

Novartis personnel (or designated CRO) will review the data entered by investigational staff for completeness and accuracy. Electronic data queries stating the nature of the problem and requesting clarification will be created for discrepancies and missing values and sent to the investigational site via the EDC system. Designated investigator site staff are required to respond promptly to queries and to make any necessary changes to the data.

Concomitant treatments and prior medications entered into the database will be coded using the World Health Organization (WHO) Drug Reference List, which employs the Anatomical Therapeutic Chemical classification system. Medical history/current medical conditions and adverse events will be coded using the Medical Dictionary for Regulatory Activities (MedDRA) terminology.

Dates of screenings, randomizations, screen failures and study completion, as well as randomization codes and data about all study treatment (s) dispensed to the participant and all dosage changes will be tracked using an Interactive Response Technology (IRT). The system will be supplied by a vendor, who will also manage the database. The data will be sent electronically to Novartis (or a designated CRO) at specific timelines.

Each occurrence of a code break via IRT will be reported to the clinical team and monitor. The code break functionality will remain available until study shut down or upon request of Novartis.

Once all the necessary actions have been completed and the database has been declared to be complete and accurate, it will be locked and the treatment codes will be unblinded and made available for data analysis/moved to restricted area to be accessed by independent programmer and statistician. Any changes to the database after that time can only be made after written agreement by Novartis development management.

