2.2 Analysis sets

For all analysis sets, participants will be analyzed according to the study treatment(s) received.

The safety analysis set will include all participants who received any study drug.

The PK analysis set will include all participants with at least one available valid (i.e., not flagged for exclusion) PK concentration measurement, who received any study drug and with no protocol deviations that impact PK data. Participants in the placebo arm will be excluded from PK analysis set.

The PD analysis set will include all participants with available PD data and no protocol deviations with relevant impact on PD data.

The analysis sets and protocol deviation codes are related as Table 2-1.

Table 2-1 Protocol deviation codes and analysis sets

Category Deviation code	Text description of deviation	Data exclusion
Subjects are excluded from S	Safety analysis in case of these PDs:	Exclude subject from Safety analysis set
WITH01	Subject withdrew consent but continue to receive study medication	Υ
Subjects are excluded from F	PK analysis in case of these PDs:	Exclude subject from PK analysis set
WITH01	Subject withdrew consent but continue to receive study medication	Y
CCI	CCI	Y
Subjects are excluded from F	PD analysis in case of these PDs:	Exclude subject from PD analysis sets
WITH01	Subject withdrew consent but continue to receive study medication	Υ
INCL04	Absence of history of PAH subgroups of clinical classification group 1 as defined in Protocol	Y
INCL05A	Resting mPAP is <25 mmHg, PCWP or left ventricular end diastolic pressure >15 mmHg as determined by RHC	Y
INCL06A		Pulmonary Vascular Resistance is <6 WU corresponding to 480 dynes s/cm5 as determined by RHC
INCL07	Patient doesn't have PAH of WHO Functional Class II – III	Υ
EXCL03	Patients with PH in clinical classification groups 2-5 (WHO) and any PAH group 1 subgroups not covered by IE 4	Y
CCI	CCI	Y

Protocol deviations mentioned above, and analysis sets will be reviewed in the data review meeting to decide inclusion or exclusion of participant(s) from analyses sets. Decisions regarding the exclusion of participants and/or participant data from analyses will be made prior to final database lock (DBL).

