2.13 Interim analysis

An unblinded interim analysis (IA) will be carried-out when approximately 20 participants complete the treatment period (Week 25).

This IA will be performed primarily to assess futility (non-binding) on PVR endpoint. The study may be stopped for futility if the posterior probability of the treatment effect no better than placebo is above 60%. Also, analysis for secondary efficacy endpoints, including right heart catheterization results, PROs, NT-proBNP, 6MWD, and TTCW will be performed as described in Section 2.6.

Safety parameters including clinical safety laboratory, ECG, vital signs, and adverse events will be listed and descriptively summarized by treatment and visit/time, if appropriate. More detailed description of the analyses as described in Section 2.7 will be conducted. The study will be stopped if there are three or more (in different participants) similar study-treatment (LTP001) related SAEs that are not related to worsening of PAH (i.e., lack of efficacy by LTP001)

Additional interim analyses may be conducted to support decision making concerning the current clinical study, the sponsor's clinical development projects in general or in case of any safety concerns. Unblinded interim analysis results will be reviewed by the clinical team.

3 Sample size calculation

Approximately 44 participants including dropouts are planned to be randomized in a 3:1 ratio to receive LTP001 vs. placebo on top of SoC. dropout rate is considered to be around 10%.

The sample size calculation was based on the primary endpoint of change from baseline in PVR at Week 25. The criterion for this calculation is based on dual criteria:

- 1. An average change from baseline for PVR over placebo is 100dyn·s·cm⁻⁵ and
- 2. 90% level of proof that the change from baseline for PVR in the LTP001 group is better than placebo.

With a non-informative prior for the LTP001 group, and the obtained weakly informative prior for the placebo group, a sample size of 40 (3:1 ratio of LTP001: placebo) provides approximately 84% chance (power) of meeting the success criterion if the true treatment effect over placebo is 200 dyn·s·cm⁻⁵.

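### The trial statistician's DMC seat contradicts the DMC's stated independence and the statistician's pre-interim blinding; separately, exclusions from the primary analysis set may stay open after the unblinded interim review

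*Protocol*

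**What the plan says.** **DMC membership.** Protocol 10.3.1 sets up a DMC "which will function independently of all other individuals associated with the conduct of this clinical trial". The note that follows states that "the trial statistician will be employed as a member of the DMC". The protocol glossary, defining the Clinical Trial Team (CTT), says: "Examples of team members include the Study Lead, Medical Monitor, Trial Statistician etc".

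**Blinding.** Under Protocol 6.5 the CTT, among others, "will remain blinded to the identity of the treatment from the time of randomization until database lock except for unblindings listed in Table 6-3". The same section says that DMC members are unblinded according to the DMC charter, and that the CTT may produce and look at unblinded reports at the interim.

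**Interim.** Both documents plan an unblinded interim when about 20 participants have completed Week 25. SAP 2.13 adds: "Unblinded interim analysis results will be reviewed by the clinical team".

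**Exclusions.** SAP 2.5.2 runs the primary PVR analysis on the PD analysis set. SAP 2.2 defines that set partly by the absence of deviations with a relevant effect on PD data, lists deviation codes in Table 2-1, and sends deviations and analysis sets to a data review meeting. On timing it says only: "Decisions regarding the exclusion of participants and/or participant data from analyses will be made prior to final database lock (DBL".

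**The concern.** There are two separate problems.

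The first is internal consistency. A committee cannot be independent of everyone involved in the trial while one of its members belongs to the sponsor's trial team. The same person would also be a DMC member, eligible for unblinding early, and a statistician whom the blinding plan keeps blinded until the interim. The protocol does not say which rule governs. At stake are the DMC's claim to independence and the blind of the person likely to influence analysis decisions most.

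The second is operational bias. The PD set determines who counts in the primary analysis, and part of its definition is judgement. If those judgements can be made by people who have seen treatment assignments and PVR results for the interim participants, the exclusions can no longer be shown to be independent of outcome. The placebo arm is expected to have only about 10 completers, so single decisions matter.

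**Working it through.** The documents state no figure on this point, so there is none to reproduce. The check is a comparison of texts, followed by one illustration of size.

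**1. DMC membership against Table 6-3**

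| Row of Protocol Table 6-3 | List generated | Allocation and dosing | Single-participant safety event | Interim |
|---|---|---|---|---|
| Statistician, programmer, data analysts | blinded | blinded | may be unblinded | may be unblinded |
| Independent committees for interim results | blinded | may be unblinded | may be unblinded | may be unblinded |
| All other sponsor staff | blinded | blinded | may be unblinded | may be unblinded |
| Unblinded sponsor staff | blinded | may be unblinded | may be unblinded | may be unblinded |

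A trial statistician on the DMC falls under the first two rows at once. They disagree on allocation and dosing, the stage that covers treatment before the interim. Protocol 10.3.1 has the DMC look at safety and key efficacy data at set intervals, so access before the interim is plausible. The conflict with independence needs only the two consecutive sentences of 10.3.1 and the glossary entry.

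**2. Interim access against the blinding rule**

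Protocol 6.5 makes CTT blinding subject to Table 6-3, and the table allows statisticians and other sponsor staff individual-level unblinding at the interim. SAP 2.13 agrees. There is no contradiction here.

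**3. Order of events**

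- Interim: about 20 of about 40 completers, 20/40 = one half.
- PD-set decisions: any time up to final database lock (SAP 2.2).
- Requirement that the deciders be blinded, or that decisions on interim participants precede the interim: none in either document.

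So the plan permits exclusions to be decided after unblinded PVR results have been seen. It does not say that they will be.

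**4. What one placebo exclusion can do**

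Inputs:
- 40 completers at 3:1 give 10 on placebo.
- The placebo prior has SD 86.7 dyn·s·cm⁻⁵ and is worth about 8 participants (Protocol 12.4.2, SAP 2.5.2).
- Neither document states a participant-level SD. The prior implies 86.7 × √8 ≈ 245, which is taken as an assumption.
- Covariates are ignored.

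Let the excluded participant lie D = 245 from the placebo mean.

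- Without borrowing: shift = D/9 = 245/9 ≈ 27.
- With a prior worth 8 participants, centred at the observed mean: shift = (9/17) × (D/9) = D/17 = 245/17 ≈ 14.

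Range: for a general SD the prior is worth SD²/86.7² participants.

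- SD 200: 200/9 ≈ 22 unborrowed. The prior is worth 40,000/7,516.9 ≈ 5.3, so 200/(9 + 5.3) ≈ 14 borrowed.
- SD 300: 300/9 ≈ 33 unborrowed. The prior is worth 90,000/7,516.9 ≈ 12.0, so 300/(9 + 12.0) ≈ 14 borrowed.

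Against the 100 dyn·s·cm⁻⁵ success criterion (Protocol 12.8.1, SAP 3), D = 245 gives 27% unborrowed and 14% borrowed.

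**The case against.** **The charter may settle the statistician's role.** Protocol 10.3.1 leaves composition and responsibilities to a charter that is not available here. It could make the role non-voting or limited to reporting, and the statistician might then fit the row for unblinded sponsor staff. This stands to the extent that one cannot say the statistician would be unblinded at every DMC review. It does not remove the conflict, because the protocol says member without qualification, directly after claiming independence.

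**Internal review is a declared choice.** A reader might infer that clinical-team review of interim results breaks the promise in Protocol 6.5 that the "Novartis Clinical Trial Team (CTT) will remain blinded to the identity of the treatment". It does not: that sentence goes on to except Table 6-3. The trial is titled participant- and investigator-blinded, is a Phase IIa proof of concept, and has non-binding futility as the interim's main purpose. This objection stands in full.

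**The route to bias is narrow.** The legible PD-set codes in SAP Table 2-1 are one consent-withdrawal code and five eligibility codes; a further row is blacked out. None of the legible codes is defined by Week 25 PVR change. The alternatives if normality fails appear under sensitivity analyses, so they are not written as replacing the primary analysis. This narrows the risk, but the judgement of relevant effect on PD data and the discretion of the data review meeting remain.

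**Who decides, and when, is not stated.** A reader might infer that the team that saw the interim results also holds the data review meeting, or that exclusions will follow the interim. SAP 2.2 names no attendees and sets only an outer deadline. The gap is that nothing rules either out.

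**The figures do not measure the DMC problem.** Correct. They show sensitivity to one exclusion, whoever makes it.

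**Conclusion.** The contradiction in Protocol 10.3.1 is real. The trial statistician's membership conflicts with the independence sentence before it, given the glossary, and with the statistician row of Table 6-3 before the interim. It has no numerical size and rests on no assumption beyond the protocol's own definitions.

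The second part holds only as an operational-bias risk: unblinded results are reviewed at about half the completers while primary-set exclusions may remain open and need not be made blind. The documents do not support a stronger claim that exclusions will be decided by unblinded people, or that sponsor-team blinding is breached.

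The 27 and 14 dyn·s·cm⁻⁵ figures are illustrations for one placebo participant at one SD. Both rest on the assumed SD of 245, and the 14 also on a prior centred at the observed placebo mean. They are not estimates of bias. The point should be corrected, but it does not invalidate the design.

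**What to change.** - **Protocol 10.3.1:** delete the note, or restate the role as a statistician outside the CTT, for example from the unblinded sponsor staff row of Table 6-3, who takes no part in the data review meeting. Align the charter and Table 6-3. Protocol 11.2 is not a ready source for this role: its data "accessed by independent programmer and statistician" concern access once the database is locked.
- **SAP 2.2:** require deviation classification and PD-set decisions for the interim participants to be documented before the interim unblinding. Require later decisions to be made without access to treatment codes or individual unblinded data. The listed eligibility codes concern entry criteria, so they can be settled early.
- **SAP 2.13:** the planned clinical-team review can stay.

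**Cost:** protocol, charter and SAP wording, one earlier data review step, and some separation of roles. The documents give no staffing, so whether an additional statistician is needed cannot be judged from them. No participant procedure changes.

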## 11 **Data Collection and Database management**

#### 11.1 Data collection

All other data captured for this study will have an external originating source (either written or electronic) with the eCRF not being considered as source.

All data should be recorded, handled, and stored in a way that allows its accurate reporting, interpretation, and verification.

Designated investigator staff will enter the data required by the protocol into the Electronic Case Report Forms (eCRF). The eCRFs have been built using fully validated secure webenabled software that conforms to 21 CFR Part 11 requirements, Investigator site staff will not be given access to the EDC system until they have been trained. Automatic validation programs check for data discrepancies in the eCRFs, allow modification and/or verification of the entered data by the investigator staff.

The investigator/designee is responsible for assuring that the data (recorded on eCRFs) (entered into eCRF) is complete, accurate, and that entry and updates are performed in a timely manner. The Investigator must certify that the data entered are complete and accurate.

After final database lock, the investigator will receive copies of the participant data for archiving at the investigational site.

All data should be recorded, handled, and stored in a way that allows its accurate reporting, interpretation, and verification.

## 11.1.1 Data collection for offsite procedures

The OHPs will enter data at off-site visits into electronic source documentation forms contained in an eSource DDC platform, which has been validated for use in clinical research. Where paper source documentation exists, images of documentation will be uploaded electronically into the same platform as certified copies, and the original documentation will then be sent to the investigator.

Data contained in the platform are available to site and sponsor staff based on role-based access and permissions and will be stored in a robust and secure cloud-based back-end environment. Only sponsor staff who are responsible for field monitoring activities will have access to the source data, which may include some personally identifiable information, consistent with the access that is provided to a field monitor in a traditional onsite clinical trial model.

Relevant data in the eSource DDC platform may be manually transcribed by site staff into the study EDC system.

Certified copies of data in the eSource DDC platform will be provided to investigator and/or site personnel, and promptly and regularly uploaded into the participant's medical records, according to local guidelines.

Investigators will have continuous, near real time access to this study and all participant records within this study in the eSource DDC platform, with the ability to add, edit, review and sign forms within participant records.

The platform maintains a secure, GCP-compliant audit trail and uses measures such as encryption and access controls to ensure that data privacy and security is maintained.

